2.3 Missing Data Conventions

No missing value imputation will be used in this analysis. All analyses will be based on the observed data.

2.4 Interim Analyses

After the injection, imaging, and quantitation of a total of 4 subjects in Arms 1 and 2 combined, an interim analysis (Interim Analysis 1) was held for the review of quantitative TUV results and assessment of imaging parameters and logistics. A second interim analysis was held after a total of 30 subjects (and at least 15 RA subjects) in Arms 1 and 2 were injected, imaged, and quantified for the review of inter- and intra-subject TUV variation to contribute to the power analysis of a future Phase 3 study and/or to terminate the study on grounds of data sufficiency.

After 15 subjects in Arm 3 completed Visit 4, an interim analysis (Interim Analysis 3) was performed to estimate the distribution of treatment effects on TUV and to optimize the TUV metric based on the interim data from all three arms.

Interim analysis plans (IAPs) were written and approved for the second interim analysis of Arms 1 and 2 and for the third interim analysis of all three study arms.

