In diagnostic radiology, quantitative imaging provides a layer of clinically meaningful information beyond that of qualitative interrogation. The Radiological Society of North America (RSNA) defines quantitative imaging as “the extraction of quantifiable features from medical images for the assessment of normal or the severity, degree of change, or status of a disease, injury, or chronic condition relative to normal. Quantitative imaging includes the development, standardization, and optimization of anatomical, functional, and molecular imaging acquisition protocols, data analyses, display methods, and reporting structures. These features permit the validation of accurately and precisely obtained image-derived metrics with anatomically and physiologically relevant parameters, including treatment response and outcome, and the use of such metrics in research and patient care.” ([RSNA 2018](#))

In nuclear medicine, the SUV (standard uptake value) is an established quantitative imaging metric for the assessment of disease-related activity across a variety of neurological, cardiovascular, oncological, and immunological conditions. For example, in 18F-labeled fluoro-2-deoxyglucose positron emission tomography (18F-FDG PET) imaging, SUV is used to measure the proliferative activity of malignant tumors in various cancers through the quantification of FDG uptake using the following parameters: r , the radioactivity activity concentration [kBq/mL] measured by the PET scanner within a region of interest (ROI), a' , the decay-corrected amount of injected radiolabeled FDG [kBq], and w , the weight of the patient [g], such that such that $\text{SUV} = \frac{r}{(a'/w)}$. ([Kinahan 2010](#))

Based on the clinical utility of SUV in 18F-FDG PET imaging, Navidea pursued the development of the TUV to quantify CD206 activity on planar gamma camera imaging. TUV considers the fundamental principles of SUV and introduces modifications to account for inter- and intra-patient variability and disease pathobiology. After the evaluation of several formula permutations, Navidea has established TUV as a metric for the measurement of joint-specific CD206 activity in RA through the quantification of Tc 99m tilmanocept uptake using the following parameters: \bar{x} , the decay-corrected average pixel intensity of a ROI, and B , the

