3 INVESTIGATIONAL PLAN

3.1 Overall Study Design and Plan

This is a prospective, open-label, multicenter, single and repeat-dose study designed to evaluate the reliability and sensitivity of TUV assessments in HCs and subjects with active RA. Subjects will be enrolled in 1 of 3 study arms (Table 4) with distinct timelines, study procedures, and study durations in accordance with Arm-specific eligibility requirements.

Table 4 Study Arms

Arm	Subjects	Evaluation(s)
1	HC subjects clinically free of any inflammatory disease and/or joint pain	Image Re-image
2	Subjects with clinically diagnosed active RA who have been on stable anti-rheumatic therapy	Image Re-image Test Re-test
3	Subjects with clinically diagnosed active RA who are candidates for initiation of, or change to, a new anti-TNF α bDMARD treatment.	Sensitivity Clinical Concordance

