8.4.1.3 Tilmanocept Uptake Value (TUV)

TUV is a quantitative imaging metric used to characterize the amount of CD206 activity on planar imaging. Results from a prior Phase 1 and 2 study have demonstrated that TUV is a sensitive and specific predictor of visually interrogated Tc 99m tilmanocept localization in joint regions with presumed inflammatory macrophage activity. A per-joint TUV (TUV_{joint}) relative ratio will be calculated for the each of the 22 DAS-28 joints located in the hands and wrists. A subject-level global TUV (TUV_{global}) assessed across the 22 joints will be used as an indication of overall disease burden.

For all subjects, delegated trained imaging scientists blinded to all clinical subject information will perform semi-automated ROI drawing on whole body planar images and static images of the bilateral hands and wrists to derive relevant count statistics, which are input parameters for joint-specific (TUV_{joint}) and global (TUV_{global}) TUVs. TUV metrics are further described in the NAV3-31 Statistical Analysis Plan.

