2.2 Analysis Populations

The following analysis populations will be used in the study:

Safety Population – The safety population includes all patients that have been enrolled in the study and injected with at least one dose of Tc 99m tilmanocept.

Intent-to-Diagnose (ITD) Population – The ITD population includes all patients that have been enrolled in the study, injected with Tc 99m tilmanocept, and received all imaging and evaluations necessary for the primary endpoint(s) appropriate to their respective arm.

Per Protocol (PP) Population: The PP population will include all ITD subjects without major protocol violations. All protocol deviations will be classified as major or minor prior to database lock.

All efficacy analyses will be carried out on the ITD and PP populations with the ITD population being the primary analysis set. All analyses of safety data and baseline subject characteristics will be carried out on the safety population. A data listing displaying the patients excluded from each population will be created, as shown in Appendix B.

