4.2 Analysis of Efficacy Variables

4.2.1 Primary Efficacy Variables

Primary Endpoints for Arms 1 and 2

All TUV data will be analyzed with summary statistics (mean, standard deviation, n, minimum, median, maximum) by study arm and joint.

Precision endpoints will be assessed estimating the mean, standard deviation, n, minimum, median, and maximum of the signed differences (CFB). The RMSD will be calculated

$$RMSD = \frac{1}{n-1} \sum_{k=1}^n (y_k - w_k)^2$$

where y_k and w_k are the measurements at the two timepoints and k represents the subject number. A 95% confidence interval for the RMSD based on Normal theory will be provided, as will a 95% bootstrap confidence interval based on $N = 5000$ bootstrap samples. Timepoints analyzed in this way will include the 60 minute A and B scans, the 180 minute A and B scans, and the difference between the 60 and 180 minute A scans. These will be done for all joints assessed and for TUV_{global} . (These analyses were completed to the sponsor's satisfaction in IA-3.)

Primary Endpoint for Arm 2 Only

The longitudinal (8-day) variation of TUV will be analyzed for each DAS28 joint and globally. The signed differences will be analyzed with descriptive statistics and the RMSD will be calculated as defined for Arm 2 above. A 95% confidence interval for the RMSD based on Normal theory will be provided, as will a 95% bootstrap confidence interval based on $N = 5000$ bootstrap samples will be computed, and 95% confidence limits for its value will be provided. This will be done for TUV_{joint} for all evaluated joints and TUV_{global} in the 60 minute images using the "A" image at baseline. The fraction of unsigned ΔTUV_{global} values less than 7.5% will be summarized in a frequency table and an exact binomial test of the hypotheses described in Section 1.3 will be included for each timepoint.

Primary Endpoints for Arm 3 Only

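### Interim analysis 3 tuned the TUV metric on subjects who are reused, with no separation or correction, in the final Arm 2 test and Arm 3 results, so these can be optimistic by an amount the documents do not let us calculate

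*SAP*

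**What the plan says.** SAP 2.4 describes IA-3 in the past tense: "After 15 subjects in Arm 3 completed Visit 4, an interim analysis (Interim Analysis 3) was performed". It gives two aims: to estimate the distribution of treatment effects on TUV, and "to optimize the TUV metric based on the interim data from all three arms". Protocol 9.5.6 had planned this look.

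The final analyses do not set those subjects apart. SAP 2.2: "All efficacy analyses will be carried out on the ITD and PP populations with the ITD population being the primary analysis set". On these sets the plan runs:

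- **Arm 2** (SAP 4.2.1): "an exact binomial test of the hypotheses described in Section 1.3 will be included for each timepoint". The null is that at most 0.80 of subjects have an 8-day change under 7.5%; SAP 1.3 sizes N = 38 for this test.
- **Arm 3 correlations** (SAP 4.2.1): Kendall correlations of the week-5 TUV change with week-12 and week-24 clinical changes, with 95% intervals.
- **Arm 3 prediction** (SAP 4.2.2 and the Table 44 shell): PPV, NPV and overall accuracy with exact 95% intervals, plus p-values for PPV and NPV against 0.6.

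No section flags or excludes IA-3 subjects, or gives a correction, combination test or cross-validation. Nor do the documents state how many candidate metrics were compared, by what rule, how many Arm 2 subjects were in, or how many Arm 3 subjects had week-12 or week-24 outcomes. SAP 2.4 mentions an approved interim analysis plan for IA-3, which is not among the documents.

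**The concern.** Choosing a measurement by looking at results, and then testing it in the same people as though it had been fixed beforehand, rewards chance. A candidate that happened to look stable, or happened to track response, in the interim subjects carries that luck into the final analysis.

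For Arm 2 the exact p-value would lose its nominal meaning, and the same holds for the PPV and NPV p-values. For Arm 3, where the primary result is an estimate, correlations and predictive values would mix development and validation subjects and read too favourably as a guide to new patients. SAP 2.4 anticipates a Phase 3 study, so that optimism could pass into its planning.

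**Working it through.** **1. Who is reused.** Arm 3: 15 of 29 planned subjects triggered IA-3, so 29 − 15 = 14 lie outside it if all 15 remain evaluable. Arm 2: no count is given. SAP 2.4 supplies a floor from the preceding look: "A second interim analysis was held after a total of 30 subjects (and at least 15 RA subjects) in Arms 1 and 2". The Arm 2 count is therefore somewhere from 15 to 38. SAP 4.2.1 adds that the Arm 1–2 same-day precision analyses were completed in IA-3, which suggests a high count but does not fix it.

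**2. The plan's own Arm 2 figure.** SAP 1.3 gives N = 38 and power 0.80, without alpha or an alternative. Assuming one-sided 0.05, the exact rule is 35/38 or more:

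- P(X ≥ 35 | n = 38, π = 0.80) = 0.0387, whereas P(X ≥ 34) = 0.0986.
- P(X ≥ 35 | n = 38, π = 0.94) = 0.808.

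So N = 38 is attainable with π near 0.94. At one-sided 0.025 the rule is 36/38 or more (size 0.0113).

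**3. Arm 2 with selection (assumed model).** K candidates all have true π = 0.80. The one with most successes among the first m Arm 2 subjects (m = 15 to 38) is chosen, and all 38 are tested. Pairwise latent correlation between candidates is 0.5 or 0.8; 20,000 simulated trials.

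| K | rejects at ≥35/38 | rejects at ≥36/38 |
|---|---|---|
| 1 (fixed, exact) | 0.039 | 0.011 |
| 3 | 0.068–0.104 | 0.021–0.035 |
| 5 | 0.085–0.157 | 0.028–0.050 |

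Uncorrelated candidates would take the 35/38 upper ends to 0.115 and 0.176.

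**4. Arm 3 with selection (assumed model).** K candidate changes are unrelated to response. The largest Kendall tau in the first 15 is chosen, all 15 being given an outcome, and tau is reported in 29. With candidate correlation 0.5–0.8:

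- Mean tau in all 29: 0.05–0.07 for K = 5 and 0.07–0.10 for K = 10, against a true 0.
- Mean tau in the 14 not used: about 0.
- For scale, the null standard error at n = 29 is √[2(2·29+5)/(9·29·28)] = √(126/7308) = 0.131.
- Share of trials with |tau| above 1.96 × 0.131 = 0.257: 5–7% (K = 5) and 7–9% (K = 10), against 5%.

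For a prediction rule with true accuracy 0.60 selected the same way (candidate correlation 0–0.8), apparent accuracy in 29 is 0.647–0.675 for K = 5.

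**5. How far this depends on the assumptions.** If the Arm 3 metric is chosen on mean TUV change alone, with response independent, mean tau is 0.00 and rejection 4.4–5.0%: no inflation. If only 5 or 8 of the 15 had outcomes at IA-3, rejection for K = 5 is 4.8–5.8%.

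**6. What a hold-out leaves in Arm 2** (one-sided 0.05):

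- 15 used, 23 left: rule ≥22/23, size 0.040, power 0.679 at π = 0.95, against 0.880 with all 38.
- 20 used, 18 left: rule 18/18, power 0.95^18 = 0.397.
- 30 used, 8 left: 0.8^8 = 0.168, so rejection is impossible.
- Fewest that can reject at all: 14, since 0.8^14 = 0.044 but 0.8^13 = 0.055.

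**The case against.** The strongest reply is that nothing shows selection on the tested outcomes. IA-3's other stated aim concerns the size of TUV change, and step 5 shows that tuning on that alone need not bias the Arm 3 correlations. The trigger was Visit 4 (week 5), so it guarantees no week-12 or week-24 outcome; SAP 2.5 lists a week-12 CDAI correlation, so some may have existed, but no number is given. This stands, and it is why the effect is stated conditionally.

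Other defences stand in part. IA-3 was planned and had an approved plan, but planning a selection step does not make its subjects independent of the later test. Image analysis was by "delegated trained imaging scientists blinded to all clinical subject information", which guards against reader bias, not against choosing a formula on observed results. The trial is a non-randomised Phase 2b study seeking a preliminary understanding (Protocol 3.1.3.3); even so, the SAP prints p-values against 0.80 and 0.6 and labels none of them developmental.

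Some stronger readings are tempting but unsupported:

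- *Several candidates are documented.* Protocol 1.1 says "After the evaluation of several formula permutations", but that describes development before this study, not IA-3.
- *IA-3 replaced the reference region.* Protocol 1.1 uses the cerebral vasculature and SAP 2.5 the hand; no section attributes the change to IA-3.
- *The Arm 3 correlation has an inflated false-positive rate.* That endpoint is an estimate with an interval; the issue there is optimism and undercoverage.
- *All concordance tables are affected.* Tables 62–65 use ACPA alone and contain no TUV.

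**Conclusion.** The structural defect is established from the documents without any assumption: the metric was optimised on subjects who re-enter the final Arm 2 and Arm 3 analyses with no separation or correction. It does not follow that the results are inflated. They can be, if repeatability or response influenced the choice, and a reader of the SAP cannot rule this out.

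The illustrated sizes are worst cases, because they select on the very outcome later tested. They rest on assumed K, correlation between candidates, interim counts and Arm 2 alpha. On those terms the Arm 2 error rate at 35/38 could about double or triple for K = 3 and rise roughly two- to fourfold for K = 5. The Arm 3 shift in tau is below one null standard error (0.131), and smaller still if few outcomes were available at IA-3.

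**What to change.** In SAP 2.4 and 4.2:

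1. Flag every subject whose data were used in IA-3. State from the interim analysis plan the candidates compared, the selection rule and the number of subjects with each outcome.
2. Report the Arm 3 primary correlations and the TUV-based concordance tables (44–61) also for subjects not in IA-3 (14 of 29 planned). Call this the validation result and label the all-subject results as development results. Tables 62–65 need no split.
3. Report Table 9 also in Arm 2 subjects not in IA-3, where enough remain. Otherwise label its p-value descriptive. Add the TUV definition in force before IA-3 only if stored counts allow it: SAP 1.2 mentions a brain read for interim analysis 2 only, so those counts may not exist for later subjects.

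The cost is one flag, repeated tables and SAP wording, with no new patients. The downside is real: validation intervals will be wide, the Arm 2 hold-out may be too small to test, and the headline figures may be less favourable.

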2.5 Calculation of TUV

All calculations are done on a reader-specific basis. That is, there is no statistical aggregation of the reader results.

Calculating Joint TUV

For an individual joint, TUV_{joint} is defined as the average pixel intensity of the joint divided by the average pixel intensity of the hand, right or left and anterior or posterior, (includes the region from one wrist region of interest (ROI) diameter above the wrist ROI down to the fingertips).

Calculating Global TUV

For each independent blind reader, determine the average TUV_{joint} and 95% prediction interval of both the anterior and posterior views of the wrists, MCPs, and PIPs in healthy individuals (NAV3-31 Arm 1). For all following calculations, reader specific average TUV_{joint} and 95% prediction intervals will be used.

For each RA subject do the following.

Step 1: Calculate TUV_{joint} for each of the 22 DAS 28 joints for which data are collected.

Step 2: Identify all imaged joints with $TUV_{joint} >$ upper limit of normal for the anatomically similar joint and view. These will be referred to as inflamed joints (IJ). Each joint has an anterior and posterior view: a joint is considered an IJ if either view has a TUV_{joint} higher than the upper bound from the normative data set.

Step 3: Calculate the macrophage-involved contribution (MI) to Tc 99m tilmanocept localization for each IJ. This is done by expressing the TUV for the IJ as a fractional change from the mean TUV for the anatomically equivalent joint and view. That is, if TUV_{joint} and \bar{H}_{joint} represent the joint and view specific TUV and the mean TUV for the anatomically equivalent joint and view from the normative data set respectively, the macrophage contribution to TUV is MI_{joint} :

$$MI_{joint} = \frac{TUV_{joint} - \bar{H}_{joint}}{\bar{H}_{joint}}$$

Step 4: TUV_{global} is the total of the macrophage-involved contributions for the IJs. (Note that MI_k is effectively 0 if TUV_{joint} is less than or equal to the upper limit of normal from the normative data set.) That is,

$$TUV_{\text{global}} = \sum_{\text{All IJs}} MI_{IJ},$$

$$TUV_{\text{global}} = \sum_{k=1}^{22} MI_k.$$

The change in TUV_{global} ($\Delta TUV_{\text{global}[5w]}$) is the $\Delta\%$ from baseline ($TUV_{\text{global}[b]}$):

$$\Delta TUV_{\text{global}[5w]} = 100 \cdot \frac{TUV_{\text{global}[5w]} - TUV_{\text{global}[b]}}{TUV_{\text{global}[b]}}.$$

Arms 1 and 2:

Precision endpoints for both arms will be assessed estimating the mean, standard deviation, n, minimum, median, and maximum of the signed differences (change from baseline) of TUV for each evaluated DAS28 joint. The RMSD will be calculated using the following equation:

$$RMSD = \sqrt{\frac{1}{n-1} \sum_{k=1}^n (y_k - w_k)^2}$$

where y_k and w_k are the measurements at the two timepoints (for example, the two scans at 60 minutes, the two scans at 180 minutes, or the first 60-minute scan and the first 180-minute scan) and k represents the subject number. A 95% confidence interval for the RMSD based on Normal theory will be provided, as will a 95% bootstrap confidence interval based on $N = 5000$ bootstrap samples. Box-and-whisker plots of TUV will be provided by arm at each timepoint for each joint, pooling small joints (MCPs and PIPs) and all joints bilaterally. Joints will not be pooled by type or bilaterally in IA 3.

ΔTUV will be summarized with descriptive statistics as the signed difference. If T_1 represents the observed TUV at the first time point and T_2 the observed TUV at the second time point, then

$$\Delta TUV = T_2 - T_1.$$

Arm 1 Only:

The distribution of TUV_{joint} in healthy controls will be summarized by time point for global TUV and each evaluated DAS28 joint with the number of joints, mean, standard deviation, 80th and 90th percentiles, the median, and 95% prediction limits for a future observation of that type at that time point. Joints will not be pooled. Box-and-whisker plots of the data will be presented by joint and time point. A scatter plot matrix for the three readers will be provided on a joint-specific basis showing the relationship between the reader TUV for the A and B scans.

Arm 2 Only:

The longitudinal precision of TUV_{joint} will be analyzed for each evaluated DAS28 joint. The signed differences will be analyzed with descriptive statistics and the RMSD will be calculated as defined for Arms 1 and 2 above. A 95% confidence interval for the RMSD based on Normal theory will be provided, as will a 95% bootstrap confidence interval based on $N = 5000$ bootstrap samples. Joints will not be pooled by type or bilaterally. A scatter plot matrix for the three readers will be provided on a joint-specific basis showing the relationship between the reader TUV for the A and B scans.

Arm 3 Only:

The Kendall rank correlation between $\Delta TUV_{global[5w]}$ with $\Delta CDAI_{12w}$ will be computed and a 95% confidence interval for its value will be computed using Fisher's Z-transformation. Similarly, the Kendall rank correlation between $\Delta TUV_{global[5w]}$ with changes from baseline in each of the ACR Response Criteria components at 12 weeks (tender joint count (TJC), swollen joint count (SJC), patient assessment of global disease activity, rheumatologist assessment of global disease activity, patient assessment of pain, patient assessment of physical function, and acute-phase reactant value) will be computed and a 95% confidence interval for its value will be computed using Fisher's Z-transformation.

2.6 Study Center Considerations in the Data Analysis

A study center is defined as a treatment administration site or group of treatment administration sites under the control and supervision of the same Principal Investigator (PI). There will be no selective pooling of study centers.

2.7 Documentation and Other Considerations

The data analyses described in this SAP will be conducted using SAS[©] Software, version 9.4 or later.

3.0 Analysis of Baseline Patient Characteristics

Baseline and demographic characteristics of the safety population will be summarized by subject arm and overall. Continuous variables (age, height, weight, and time from diagnosis of RA) will be summarized via mean, standard deviation, minimum, maximum, and number of non-missing responses. Categorical variables (gender, race, and ethnicity) will be summarized via counts and percentages.

A detailed listing of baseline data for each patient in the safety population will also be provided, as shown in Appendix B.

4.0 Analysis of Efficacy

4.1 Description of Efficacy Variables

The efficacy variables for this study are as follows:

- Quantitative determination of TUV_{joint} and TUV_{global} at Day 0, Day 8, Week 5, Week 12, and Week 24 as appropriate to the subject's study arm.
- Qualitative determination of tilmanocept localization in planar images and SPECT/CT images of the bilateral hands and wrists.
- Subject RA status evaluations in Arm 3 as summarized in the CDAI overall score and its subscores.
- Subject RA status evaluation in Arm 3 as summarized by the ACR Response Criteria.
- Change in TUV.

The presence of radiotracer uptake for a joint indicates the presumed presence of activated macrophages. The use of the term "localization" in this SAP is synonymous with the presence of radiotracer uptake.

TUV is defined as:

$$TUV_{joint} = \frac{\bar{X}_{joint}}{\bar{X}_{RR}};$$

where

- \bar{X}_{joint} is the average voxel intensity of a particular joint of a subject at the anterior or posterior views at 1 or 3-hours post-injection;

- \bar{X}_{RR} is the average voxel intensity of the reference region (RR) of a subject at the anterior or posterior views at 1 or 3-hours post-injection.

